10.5.2 Clinical Laboratory Parameters

Clinical chemistry, hematology and coagulation data will be summarized by hepatic function group and timepoint. Changes from baseline will be calculated. In addition, all Clinical

Chemistry, CBC, hematology, coagulation and urinalysis data outside the clinical reference ranges will be listed by parameter and hepatic function group.

Values for any clinical chemistry, hematology, coagulation and urinalysis values outside the clinical reference ranges will be flagged on the individual subject data listings. Reference ranges will be presented in the listing and used to determine either the low or high values in comparison to the reference ranges. Hemoglobin A1c Test Data will be listed by Subject.

All out of range laboratory evaluation data (including clinical chemistry, hematology, and urinalysis) deemed clinically relevant by the PI (or designee) will be listed by parameter.

10.5.3 Vital Signs

The vital signs data (including oral temperature, supine blood pressure, heart rate, and respiratory rate) will be summarized by hepatic function group and time point, together with changes from baseline. Figures of mean vital signs and mean change from baseline profiles will be presented by hepatic function group.

Vital signs values outside the clinical reference ranges will be flagged in the individual subject data listings.

Repeat and unscheduled readings will be handled as defined in [Section 10.1.2](#)

10.5.4 Electrocardiogram

The ECG data will be obtained directly from the 12-lead ECG traces. These data include the QT interval calculated using the Fridericia correction (QTcF), the PR and QT intervals, the QRS duration, and heart rate.

The ECG data along with change from baseline will be listed and summarized by timepoint.

Values for ECG parameters outside the clinical reference ranges will be flagged on the individual subject data listings.

An outlier analysis will be performed including all maximum individual postdose measurements (not the mean data), including all repeat and unscheduled readings. All incidences of QTc and QTcF (>450 and ≤ 480 , >480 and ≤ 500 , and >500 ms) will be flagged in the listings. Change of > 30 msec in QTcF will be flagged.

10.5.5 Other Assessments

PE and concomitant medications(coded using WHODrug Version 01 September 2018 Global Dictionary DDE+HD Version B3 format) will be listed by hepatic function group and time point using descriptive statistics.

All other safety assessments not detailed in this section will be listed but not summarized or statistically analyzed.

Medical history data will be presented.

10.5.6 Safety and Tolerability Statistical Methodology

No inferential statistical analyses are planned.

11 INTERIM ANALYSES

Interim reviews of safety data will be conducted for each group when the first 4 subjects from Group 2 (mild hepatic impairment subjects) are enrolled and have completed the study, when the first 4 subjects from Group 3 (moderate hepatic impairment subjects) are enrolled and have completed the study, and when the first 2 subjects from Group 4 (severe hepatic impairment subjects), are enrolled and have completed the study. Subjects will be considered to have completed the study if they have undergone all study-related assessments as described in the Schedule of Assessments, including the Follow-up phone call. These safety data will include AEs and serious AEs, vital signs, PEs, ECGs, and clinical laboratory tests. If available, PK data and matched-control healthy subject data may also be used during the review. Enrollment and dosing for remaining subjects in any group may occur after the interim data for that group are reviewed and the Covance Medical Monitor, Investigator (or designee), and Sponsor agree it is safe to proceed with dosing.

Each interim review will be a teleconference between the Covance Medical Monitor, Investigator (or designee), and/or Sponsor to discuss safety data.

Following the interim review of safety data for a group, the dose level may be decreased for the remaining subjects in any group pending discussion and agreement between the Covance Medical Monitor, Investigator (or designee), and/or Sponsor. If dosing is decreased, it will also be decreased for the impaired subjects' respective matched-control healthy subjects.

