#### 4.7. Matching Process

A matched-control healthy subject will be matched to hepatically impaired subjects (age [ $\pm 10$  years], BMI [ $\pm 20\%$ ], and sex). An individual matched-control healthy subject may be matched with up to 1 subject within each hepatic impairment group (ie, to a maximum of 3 hepatically impaired subjects across the study [1 mild, 1 moderate, and 1 severe], but to no more than 1 subject in each impairment group). A listing of the matched subjects will be included in the Clinical Study Report.

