## 8.5. Statistical Analysis of Pharmacokinetic Data

Plasma concentrations and PK parameters will be summarized by hepatic function with descriptive statistics (number, arithmetic mean, standard deviation, coefficient of variation [CV%], geometric mean, geometric CV%, median, minimum, and maximum). In addition, summary statistics for protein binding will be tabulated by hepatic function group.

The primary analysis planned for this study is to evaluate the PK of LOXO-292 after a single dose in subjects with mild, moderate, or severe hepatic impairment, compared to subjects with normal hepatic function. The following statistical methodology will be used, based on 1 to 1 matching:

An analysis of covariance (ANCOVA) will be performed on the ln transformed  $AUC_{0-t}$ ,  $AUC_{0-\infty}$ , and  $C_{max}$ . The ANCOVA model will contain a categorical factor of population for subjects with varied degree hepatic impairment (severe, moderate, and mild) and healthy matched control subjects, a categorical covariate (sex), and continuous covariates (age and BMI). Ratios of least squares means (LSM) and 90% CIs will be calculated using the exponentiation of the difference between renal function cohort LSM from the ANCOVA analyses on the ln transformed  $AUC_{0-t}$ ,  $AUC_{0-\infty}$ , and  $C_{max}$ . The specific procedures will be documented in the SAP.

All statistical calculations will be performed using SAS® Version 9.3 or greater.

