Each matched-control healthy subject (Group 1) will be demographically matched (1:1) by age (\pm 10 years), body mass index (BMI; \pm 20%), and sex to the enrolled hepatic impairment subject(s). Should another hepatic impairment subject be identified with whom an already enrolled healthy subject is demographically matched, the healthy subject may also be matched with that impaired subject as long as the impaired subject is in a different hepatic impairment group. Each subject with normal hepatic function may be matched with up to 1 subject within each hepatic impairment group.

To assess their eligibility to enter the study, potential subjects will be screened within 28 days (Days -29 to -2) and be admitted to the clinical site on Day -1 (Check-in). Replacement subjects may be enrolled only if deemed necessary by the Sponsor.

Subjects will be confined at the clinical site from the time of Check-in (Day -1) until Clinic Discharge on Day 11 upon completion of all PK and safety assessments. A Follow-up phone call will occur approximately 7 days after Clinic Discharge.

On the morning of Day 1, after at least a 2-hour fast, an oral dose of 160 mg LOXO 292 administered as two 80-mg capsules will be given with 240 mL water. No food will be allowed for up to 1 hour postdose. Glucose tablets may be administered as needed for treatment of hypoglycemia.

Figure 1 Study design schematic

ICF = Informed Consent Form; PK = pharmacokinetic.

Note: Single oral dose of LOXO-292 at 160 mg administered orally after at least a 2-hour fast.

In this study design, physical examinations (PEs), 12-lead electrocardiograms (ECGs), vital signs, How Do You Feel? inquiries, clinical chemistry panel, coagulation parameters, complete blood count, and urinalysis will be performed at Screening and at specified times during the study. All adverse events (AEs) will be recorded throughout the study (ie, from signing of the ICF until Study Completion), either as subject medical history (if the event is reported as occurring prior to signing of the ICF) or as AEs (if the event occurs after administration of LOXO-292). Between the time of ICF signing to administration of LOXO-292 only AEs assessed as related to study procedures should be reported. All serious AEs (SAEs) that develop from the time of ICF signing until Study Completion are to be reported.

Study Completion is defined as the time of the last subject's Follow-up phone call.

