10.4 Statistical Methods for Pharmacokinetic Data

10.4.1 Descriptive Statistics

Arithmetic means, %CV, SD, median, Min, Max, and n will be calculated for PK parameters separately in healthy subjects and subjects with hepatic impairment. Geometric mean and geometric %CV will be provided for all PK parameters except t_{max} . Median, min, max, and n will be calculated for t_{max} . In addition, summary statistics for protein binding will be tabulated by hepatic function group.

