10.4.2 Primary Analysis

To evaluate the effect of hepatic function group on the PK of a single dose of LOXO-292, paired t-test will be performed for each hepatic impairment group versus the normal group with respect to 1 to 1 matching. The 1 to 1 matching comparisons of interests include:

- Subjects with severe hepatic impairment versus healthy matched control subjects.

- Subjects with moderate hepatic impairment versus healthy matched control subjects.
- Subjects with mild hepatic impairment versus healthy matched control subjects.

Since the comparison groups of subjects are independent in terms of degrees of hepatic impairment and dependent based on the matching criteria, paired Proc ttest in SAS will be used for this comparison on the natural log transformed PK parameters (AUC_{0-t}, AUC_{0-∞}, and C_{max}). The 90% confidence interval for the ratio between each level of impaired hepatic function versus the matched-control healthy subject group will be presented. The normality assumption will be explored to ensure no major deviation to the assumption exists. The corresponding results along with any outliers will be evaluated and can be included in the CSR appendix as needed. Any major outliers will be investigated case by case and determine the appropriate action on how to handle them.

Example SAS code:

```
proc ttest data= logpk alpha=0.1;  
by paramcd;  
paired normal*impairment;  
run;
```

where;

paramcd = categorical variable to indicate different PK parameters

impairment = natural log-transformed PK parameters for the subjects with hepatic impairment

normal = natural log-transformed PK parameters for the healthy matched controlled subjects

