10.4.3 Analysis of Covariance

To evaluate the effect of hepatic function group on the PK of a single dose of LOXO-292In addition, an analysis of covariance (ANCOVA) will be performed on the natural log transformed AUC_{0-t}, AUC_{0-∞}, and C_{max}. The ANCOVA model will contain a categorical factor of population for subjects with various degrees of hepatic impairment (mild, moderate, and severe) and healthy matched control subjects, a categorical covariate (sex), and continuous covariates (age and BMI). The ratios of least square means (LSM) and 90% CI for the ratio of the PK parameter for each hepatic function group versus the matched normal group will be constructed using the exponentiation of the difference and the CIs from the ANCOVA analyses. These ratios will be expressed as a percentage relative to the healthy matched control cohort.

The 1 to 1 matching comparisons of interests include:

- Subjects with severe hepatic impairment versus healthy matched control subjects.
- Subjects with moderate hepatic impairment versus healthy matched control subjects.
- Subjects with mild hepatic impairment versus healthy matched control subjects.

Example SAS code:

```
proc mixed data = dataset;
class group sex;
model IPK = group sex age BMI / alpha=0.1 cl solution outpred=resids;
lsmeans group / pdiff alpha=0.1;
ods output lsmeans=lsmeans;
ods output diffs=diffs;
run;
quit;
```

Residual plots will be produced to assess the adequacy of the model.

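### The SAP allows a mid-study dose reduction but compares Cmax and AUC without dose adjustment, so a reduction in one group would bias at least one ANCOVA ratio and any unequal-dose matched pairs

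*SAP*

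**What the plan says.** SAP 11 (and Protocol 8.2) says that after a group's interim safety review "the dose level may be decreased for the remaining subjects in any group". It adds that "it will also be decreased for the impaired subjects' respective matched-control healthy subjects"; Protocol 5.2 says the same. The reviews follow the first 4 mild, 4 moderate and 2 severe subjects.

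On the analysis side:

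- SAP 10.4.2 makes the paired t-test primary, "used for this comparison on the natural log transformed PK parameters".
- SAP 10.4.3 adds an ANCOVA with the statement "model IPK = group sex age BMI". Protocol 8.5 specifies the same terms: "The ANCOVA model will contain a categorical factor of population for subjects with varied degree hepatic impairment", plus sex, age and BMI.
- SAP 10.4.1 says descriptive statistics "will be calculated for PK parameters separately in healthy subjects and subjects with hepatic impairment", with no split by dose.
- SAP 7 lists 160 mg as the only treatment for all four groups.

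On matching, SAP 6 states: "Each subject with normal hepatic function may be matched with up to 1 subject within each hepatic impairment group". Protocol 4.7 spells out that one control may therefore be matched "to a maximum of 3 hepatically impaired subjects across the study".

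**The concern.** The plan provides for a second dose level but has no analysis for it. Cmax and AUC scale with dose, so once doses differ, a ratio of raw exposures mixes the dose difference with the hepatic effect. Dose enters the SAP only through clearance and volume parameters, which are not compared inferentially.

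Lowering the matched control along with the impaired subject equalises dose within a dedicated pair. It leaves two gaps:

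- The ANCOVA has no pair term and no dose term. Every impairment group is compared with one pooled control mean, whatever doses those controls received.
- A control is dosed once but may serve partners in three groups. It may already have had 160 mg when matched to a later subject on a lower dose, or it may be lowered for one partner and so differ from another. The documents do not say how such a control is handled.

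Protocol 1.4 says the study is to inform dosing recommendations in hepatic impairment, so the ratios at risk are the study's main product.

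**Working it through.** There is no stated power or error figure to reproduce; SAP 8 bases the sample size on precedent. The check derives the bias factor and then simulates the SAP's ANCOVA.

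**Inputs from the documents**

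- Up to 8 subjects per impairment group and 8 to 16 controls (SAP 6).
- Two severe subjects complete before the review, so up to 6 of 8 could be lowered (SAP 11).
- Up to 3 partners per control, one per group (Protocol 4.7).
- Linear PK (Protocol 3.3), so exposure is taken as proportional to dose.

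**Assumptions.** Only the severe group is lowered. The lowered dose is not stated, so let r = lowered dose/160, with r = 0.5 and r = 0.75 used purely as arithmetic.

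**Control reuse.** With 24 impaired subjects and at most 16 controls, at least 24 − 16 = 8 matches reuse a control.

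**ANCOVA.** Each lowered subject's ln exposure shifts by ln r. If f is the fraction of a group at the lowered dose, the expected ratio is the true ratio × r^(f_imp − f_ctrl).

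| Controls | f_ctrl | Severe, r = 0.5 | Mild/moderate, r = 0.5 | Severe, r = 0.75 | Mild/moderate, r = 0.75 |
|---|---|---|---|---|---|
| A: 16, of whom 6 lowered | 6/16 | 0.5^(6/8 − 6/16) = 0.77 | 0.5^(−6/16) = 1.30 | 0.90 | 1.11 |
| B: 8 shared by all groups, 6 lowered | 6/8 | 0.5^0 = 1.00 | 0.5^(−6/8) = 1.68 | 1.00 | 1.24 |
| C: 8 shared, all already dosed at 160 mg | 0 | 0.5^(6/8) = 0.59 | 1.00 | 0.81 | 1.00 |

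Dividing the severe factor by the mild factor cancels the control mean and leaves r^(6/8) in every row: 0.59 for r = 0.5 and 0.81 for r = 0.75. The two factors can therefore never both equal 1, and at least one ratio is biased however the controls are arranged.

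**Paired t-test, 8 pairs.** The factor is r^(k/8) for k pairs with only the impaired subject lowered, and r^(−k/8) for k pairs with only the control lowered.

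- A: 1.00 in all groups, provided the 6 lowered controls serve only severe subjects.
- B: six unequal pairs in mild and in moderate give 0.5^(−6/8) = 1.68; severe is 1.00.
- C: six unequal pairs in severe give 0.5^(6/8) = 0.59; mild and moderate are 1.00.
- An intermediate case, k = 2: 0.5^(2/8) = 0.84 or 0.5^(−2/8) = 1.19. For r = 0.75, 0.93 or 1.07.

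**Simulation of the ANCOVA** (group, sex, age, BMI; assumed CV 40%; r = 0.5; true ratios 1; 800 runs per scenario). Raw estimates matched the table: A gave 0.77 for severe and 1.28 to 1.29 for mild and moderate; B gave 1.69 for mild and moderate; C gave 0.59 for severe. Coverage of the 90% interval fell to about 0.70 in A, 0.28 for mild and moderate in B, and 0.23 for severe in C. After dose normalisation the estimates were 0.99 to 1.00 and coverage was 0.88 to 0.92.

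With a true severe ratio of 2.00, scenario A gave 1.54 raw and 1.99 after normalisation. By the formula, scenario C would show 2 × 0.5^(6/8) = 1.19.

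**The case against.** The strongest reply is that the primary analysis is already protected. The SAP supersedes the protocol's statistical section, makes the paired test primary and calls the ANCOVA additional; the control-lowering rule exists to keep pairs comparable. Reuse of controls does not by itself create unequal pairs. In the example, 8 controls at 160 mg can serve all mild, all moderate and the 2 early severe subjects, and 6 more can serve only the lowered severe subjects: 8 + 6 = 14 controls, no unequal pair.

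That is right for the paired test if demographic matches allow it, but the plan does not require such an arrangement. Nor does it rescue the ANCOVA: with f_ctrl = 6/14, the factors are 0.5^(6/8 − 6/14) = 0.80 for severe and 0.5^(−6/14) = 1.35 for mild and moderate.

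A second reply is that CL/F is dose-corrected and summarised by geometric mean, so a reader could recover a dose-adjusted AUC0-∞ contrast. This is true, but it is descriptive, carries no interval, and does not cover Cmax or AUC0-t. SAP 10.3.1 allows extra parameters but does not require dose-normalised ones.

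Third, scenarios B and C are extremes. C conflicts with the lowering rule unless the controls were dosed earlier and then reused. That sequence is possible, because SAP 6 and Protocol 3.1 let an already enrolled control take a further match. Protocol 3.1 elsewhere speaks of matching to completed impaired subjects, where the synopsis and SAP 6 say enrolled.

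Fourth, the contingency may never have arisen. The administrative letter raising the upper age limit reports that interim doses were well tolerated, with no Grade 3 or higher toxicity. An agreed SAP deviation also remains available. These points lower the priority. They do not supply a prespecified analysis, and in an open-label study the choice could be made after PK data are seen.

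**Conclusion.** The concern holds, as a conditional gap that should be closed. If one group's dose is lowered and the SAP is followed as written, at least one ANCOVA impaired/normal ratio is biased, whatever doses the controls received. The paired test is biased only in groups containing unequal-dose pairs.

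The more ordinary case for the ANCOVA is scenario A: factors of 0.77 and 1.30 for an assumed halving, 0.90 and 1.11 for an assumed 25% cut. The values 0.59 and 1.68 mark the extremes of control sharing. Direction and affected group depend on the sharing pattern.

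The figures rest on linear PK, 6 of 8 severe subjects lowered, no change in the other groups, and an assumed reduction. Confidence is medium because the trigger may not have occurred, and because the separate table and listing shells, which might display actual dose, are not available.

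**What to change.** - **SAP 10.4.2 and 10.4.3:** state that if any subject receives a dose other than 160 mg, Cmax, AUC0-t and AUC0-∞ are multiplied by 160/actual dose before log transformation, citing the linearity asserted in Protocol 3.3.
- **SAP 10.4.1:** apply the same to the total and unbound exposure summaries.
- **Sensitivity:** repeat the paired t-test on equal-dose pairs only.
- **SAP 7 and listings:** show the actual dose.
- **Reconciliation:** SAP 11 and Protocol 5.2 must be reconciled with the control-sharing rule (Protocol 4.7, SAP 6) for a control whose partners have different doses. No dose or clinical rule is proposed here.

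The cost is short wording changes in those sections, one derived variable and one conditional table. Estimates are unchanged if no dose is lowered. The downside is reliance on dose proportionality. AUC0-t also normalises only approximately, because concentrations after a lower dose fall below the quantification limit sooner. The equal-dose-pairs analysis removes the within-pair dose difference without that assumption, at the price of fewer pairs.

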12 CHANGES FROM THE PROTOCOL SPECIFIED STATISTICAL ANALYSES

The statistical methods for analysing the PK data outlined in the synopsis and main body of the protocol (version 1.0) and have been clarified in further detail in [Sections 10.4.2](#) and [10.4.3](#), including an additional analysis suitable for the hepatic design of the trial.

13 DATA PRESENTATION

13.1 Insufficient Data for Presentation

Some of the TFLs may not have sufficient numbers of subjects or data for presentation. If this occurs, the blank TFL shell will be presented with a message printed in the center of the table, such as, "No serious adverse events occurred for this study."

